3.3.3 Exploratory endpoints

Cardiac Power Output Index (CPOi) at admission to ICU post-transplant implantation and at 6h post-operation will be recorded. The difference between CPOi within individuals at admission to ICU and 6h post-operation will be calculated. Cardiac Power Output is defined as the hydraulic energy created by the ventricles per unit time. It is the product of Cardiac Output (CO), measured by Swan Ganz, and the Mean Arterial Pressure (MAP), taking into account the filling state of the individual and indexed to body size. It has been validated as a measure of pump failure in patients with cardiogenic shock. Primary graft dysfunction is effectively the failure of the cardiac allograft to generate sufficient cardiac output and therefore it has been hypothesised that low cardiac power output after transplantation will correspond to the development of PGD and the requirement for mechanical circulatory support. CPOi on admission to ICU has been shown to be correlated with donor to recipient heart mass ratio and inversely correlated to cardiopulmonary bypass time. Previous work from Birmingham has determined a rule-in, rule-out algorithm for cardiac power index as a predictor of severe PGD and early mortality.

3.3.4 Table of endpoints/outcomes

Objectives	Outco	ome Measures	this (epoint(s) of evaluation of outcome measure (if icable)
Primary Objective:	The proportion of eligible donor		At th	e end of recruitment.
To assess the feasibility of	cardiac allografts that are			
conducting the CUSToS study.	rando	mised and that receive the		
	correct intervention.			
Secondary Objectives:	i.	The proportion of	iiv.,	, viiviii., xxi. At the end
To compare the effect of		eligible recipients who	of rec	cruitment
Custodiol-HTK solution and St		consent to take part in	vvi.	24-hours post-
Thomas' solution on the		the study.	trans	plant
outcomes of cardiac	ii.	The proportion of	ix.	30-days post-transplant
transplantation from donation		eligible donor cardiac		
after brainstem death (DBD)		allografts where		
donors.		randomisation occurs		
		according to the		
		Protocol.		
	iii.	The proportion of		
		eligible donor cardiac		
		allografts where the heart		
		is preserved in the		
		correct randomly		
		allocated solution.		
	iv.	Key outcome		
		completeness		
	v.	The development of		
		PGD, measured at 24-		
		hours post-transplant		
	vi.	Left Ventricular ejection		
		fraction, left ventricular		
		maximal posterior wall		
		thickness, maximal		

		UK
	septal wall thickness, left	
	ventricular function,	
	right ventricular function	
	and the presence/absence	
	of regional wall motion	
	abnormalities measured	
	on trans-oesophageal	
	echo immediately after	
	transplant implantation	
	vii. 30-day all-cause	
	mortality	
	viii. 6-month survival	
	ix. Development of post-	
	operative complications	
	within 30 days of	
	transplant x. Median length of initial	
	ICU stay in hours	
	xi. Median Length of initial	
	hospital stay in days	
Exploratory Objectives:	Cardiac Power Output Index,	At admission to ICU and 6 hours
To assess CPOi as an outcome	absolute differences between the	post admission to ICU
measure for predicting PGD	groups (PGD/No PGD and	
	Custodiol-HTK/St Thomas') and	
	change over time within and	
	between groups	

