- iii. Body surface area calculated using the DuBois and DuBois formula: Body Surface Area= 0.007184 x (Height(m) $^{0.725}$) x (Weight(kg) $^{0.425}$).
- iv. Mean Arterial Pressure (mmHg) on invasive intra-arterial blood-pressure monitoring at the time of Swan-Ganz measurements.
- v. Central Venous Pressure (mmHg) on invasive central venous pressure monitoring at the time of Swan-Ganz measurements.

As this is an exploratory outcome measure, with the intent to assess its utility based on real-world data, this will be assessed based on the above data being recorded on the intensive care electronic health record system. The measurements will be taken and recorded by the healthcare professional(s) looking after the participant. Where the outcome assessor transferring this data from the healthcare record to the trial database cannot find a measurement within the stipulated timeframe, this will be treated as missing data.

PGD will be determined based on the ISHLT consensus statement 2014 (2) and graded accordingly. PGD is defined as occurring within 24 hours, therefore all measurements included below must be taken within the first 24 hours after admission to ICU post-transplant procedure. Its definition requires the following variables to be recorded on the database:

F-CUSToS Protocol

Version Number 2.0; Dated 30 January 2025

- Ejection fraction on echocardiogram; where multiple measurements are taken the lowest estimate of ejection fraction recorded will be inputted to the database.
- ii. Haemodynamic variables taken at the time of a Swan Ganz measurement*:
 - (i) Central Venous Pressure (mmHg)
 - (ii) Pulmonary capillary wedge pressure (mmHg)
 - (iii)Cardiac Output (L/min)
 - (iv) Cardiac Index (L/min/m2)
 - (v) Mean Arterial Pressure (mmHg)
 - (vi)Transpulmonary gradient (mmHg)
 - (vii) Pulmonary artery systolic pressure (mmHg)
- iii. Vasoactive Inotrope Score (VIS), where VIS = dopamine [μ g kg⁻¹ min⁻¹] + dobutamine [μ g kg⁻¹min⁻¹] + 100×adrenaline [μ g kg⁻¹ min⁻¹] + 50×levosimendan [μ g kg⁻¹ min⁻¹] + 10×milrinone [μ g kg⁻¹ min⁻¹] + 10 000×vasopressin [units kg⁻¹ min⁻¹] + 100×noradrenaline dose [μ g kg⁻¹ min⁻¹].
- iv. Presence/absence of an intra-aortic balloon pump (IABP).
- v. Presence/absence of mechanical circulatory support (ECMO/LVAD/RVAD/BiVAD).

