10 STATISTICS AND DATA ANALYSIS

10.1 Sample size calculation

This is a feasibility study, so formal sample size calculation is not required. However, 50 hearts will give a 95% confidence interval of 53%-79% assuming a primary outcome rate of 66%.

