10.3.3 Secondary outcome analysis

Credible intervals for proportions:

(Such as "the proportion of eligible recipients who consent to take part in the study)
95% Jeffreys credible interval with equal-tail probabilities will be defined for the proportions of interest.

Tests of differences in proportions:

(Such as the difference in PGD rates between the two solutions of interest)

Difference between two proportions defined on independent samples will be assessed by means of exact fisher or score tests. 95% CI for the difference in proportions will be defined by inverting the score test. Logistic regressions may be considered to control for selected confounders. Penalised likelihood will be used in case of perfect separation of the binary outcome by a set of predictor levels.

Tests of independence between pairs of categorical variables:

(Such as the association between grade 3 PGD and treatment)

The independence of rows and columns of contingency table with fixed marginals will be assessed by means of Fisher's exact tests. Ordinal regressions may be considered to control for selected confounders. Partial proportional odds models will be considered if the proportional odd assumption is violated.

Test of equality of two independent means for continuous outcomes:

(Such as the equality of means of some echocardiographic parameter per treatment group)

Welch t-tests will be used to compare the means of two independent samples for continuous outcomes. Transformations (like log, box-cox) will be used in case of strong deviations to normality of the residuals within each group. Wilcoxon rank sum tests may be used as sensitivity analyses or when the comparison of medians (instead of means) is preferred. Linear regressions may be considered to control for selected confounders. Generalized Additive Models for Location, Scale and Shape models will be preferred in case of the presence of heteroscedasticity.

Test of equality of two independent means for bounded outcomes like proportions:

(Such as the association between left ventricular ejection fraction and treatment)

Welch t-tests will be used to compare the means of two independent samples for bounded outcomes like proportion. Transformations (like log, box-cox) will be used in case of strong deviations to normality of the residuals within each group. Wilcoxon rank sum tests may be used as sensitivity analyses. Beta regressions may be considered to control for selected confounders.

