10.5 Adjusted analysis

F-CUSToS Protocol Version Number 2.0; Dated 30 January 2025

As outlined above, risk adjustment for baseline value of CPOi (at admission to ICU) will be used in the linear regression for difference in CPOi between admission to ICU and 6 hours post-transplant. All linear and logistic regression models will be adjusted for confounders of interest and presented alongside single comparison tests, such as Fisher's exact test without adjustment.

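### The exploratory objective is to assess CPOi for predicting PGD, but the stated measure shows only association and does not quantify discrimination

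*Protocol*

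**What the plan says.** The exploratory row of the table in Section 3.3.4 gives the purpose as assessing CPOi as an outcome "measure for predicting PGD". The measure beside it is CPOi, "absolute differences between the" "groups (PGD/No PGD and" the two solutions), with change over time within and between groups. Section 7.7 describes the purpose in similar terms: "As this is an exploratory outcome measure, with the intent to assess its utility based on real-world data".

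The statistics section treats CPOi only as a dependent variable. For continuous variables, Section 10.3.3 states: "Welch t-tests will be used to compare the means of two independent samples for continuous outcomes". It allows transformations, rank-sum tests as a sensitivity analysis or where medians are preferred, and linear regression. The one model specific to CPOi is in Section 10.5: "risk adjustment for baseline value of CPOi (at admission to ICU) will be used in the linear regression for difference in CPOi" between ICU admission and 6 hours.

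Section 3.3.3 gives background on the marker: "Previous work from Birmingham has determined a rule-in, rule-out algorithm for cardiac power index as a predictor of severe PGD and early mortality". The protocol gives no thresholds for that algorithm and attaches no endpoint or analysis to it.

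**The concern.** The objective and the measure in one table row answer different questions. Prediction asks how often a reading would correctly sort a recipient into PGD or no PGD. A difference between groups asks whether the two distributions are centred in different places. In a small sample, a gap can be statistically significant while the distributions overlap heavily.

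The protocol names no AUC, sensitivity, specificity, predictive value or cut-off, and no model with PGD as outcome and CPOi as explanatory variable. The logistic regression in Section 10.3.3 is offered for differences in proportions, such as PGD by solution.

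What is at stake is interpretation. A report that follows the table could present a significant CPOi difference as the answer to the prediction objective without showing that discrimination may be weak.

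**Working it through.** **The plan's own figures.** The protocol gives no figure for CPOi: no standard deviation, expected difference or target accuracy. The nearest stated figure is the precision of the 50-heart sample in Section 10.1, 53% to 79% at a rate of 66%. It reproduces as a Wald interval: 0.66 ± 1.96 × √(0.66 × 0.34 / 50) = 0.529 to 0.791.

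**Inputs**
- Sample: 50 transplants (trial summary, Section 10.1).
- PGD rate: 36%, the current UK estimate in Section 7.10, so 18 with PGD and 32 without.
- Range: Section 10.2 assumes 36% in one arm and 22% in the other for the main trial. The average is 29% (about 14 against 36). A rate of 22% throughout gives 11 against 39.
- Assumption, not in the protocol: CPOi is normal with equal variance in the two groups, and the pooled t-test stands in for Welch.

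**Step 1: smallest significant difference.** In standard deviation units, d = t(0.975, 48) × √(1/n₁ + 1/n₀). For 18 against 32: 2.011 × √(1/18 + 1/32) = 2.011 × 0.2946 = 0.59.

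**Step 2: what that difference means for discrimination.** AUC = Φ(d/√2); sensitivity at 90% specificity = Φ(d − 1.2816). For 18 against 32: Φ(0.592/1.414) = 0.66 and Φ(0.592 − 1.2816) = 0.25.

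| PGD / no PGD | Just-significant d | AUC | Sensitivity at 90% specificity |
|---|---|---|---|
| 18 / 32 (36%) | 0.59 | 0.66 | 25% |
| 14 / 36 (about 29%) | 0.63 | 0.67 | 26% |
| 11 / 39 (22%) | 0.69 | 0.69 | 28% |

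At the difference detectable with 80% power for 18 against 32 (d = 0.83), the AUC is 0.72 and the sensitivity 32%. If only two thirds of 50 had data (33 recipients, 12 against 21), a just-significant result would be d = 0.74 and AUC 0.70.

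**Step 3: precision of the added estimate.** The Hanley–McNeil standard error is √{[A(1−A) + (n₁−1)(Q₁−A²) + (n₀−1)(Q₂−A²)] / (n₁n₀)}, with Q₁ = A/(2−A) and Q₂ = 2A²/(1+A). For A = 0.80 and 18 against 32: √{[0.16 + 17 × 0.0267 + 31 × 0.0711] / 576} = 0.070, so the 95% interval is 0.66 to 0.94 (±0.14). For A = 0.70 the standard error is 0.080 and the interval 0.54 to 0.86 (±0.16). With 14 against 36, an AUC of 0.80 has an interval of 0.65 to 0.95.

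**The case against.** The best counter-argument is that the choice of discrimination statistic for an exploratory marker is usually a matter for the statistical analysis plan, which is not shown. The table cell does not mention means or rule out other statistics; the t-test comes from a general list in Section 10.3.3 whose examples do not include CPOi. This stands in part: a later document could add the AUC. But the protocol does not leave the measure open. It names one, beside the objective, and that measure does not answer it.

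A reader might go further and infer that the planned comparison cannot bear on prediction at all. That is too strong. A group difference does show association, and under the normal model it maps directly to an AUC. The rank-sum test that Section 10.3.3 permits is a test of AUC = 0.5, since its U statistic divided by n₁n₀ is the empirical AUC. What is missing is the estimate and its interval.

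A reader might also infer that the plan fails to test an algorithm it relies on. Section 3.3.3 mentions the algorithm once, as background. The protocol never undertakes to validate it, gives no cut-offs, and describes its target as severe PGD and early mortality, whereas the planned contrast is any PGD against none. Leaving it out is not a contradiction.

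Finally, the AUC would not settle prediction. Section 7.7 records cardiac output, mean arterial pressure and central venous pressure both for CPOi and for determining PGD, and both CPOi readings fall inside the 24-hour PGD window. Some separation is built in. This stands as a limit on how the AUC should be read, and it applies equally to the planned group difference.

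**Conclusion.** The point holds as a minor mismatch between objective and measure. The row in Section 3.3.4 promises an assessment of prediction and specifies a measure of association. At the documented 36% PGD rate, a just-significant difference is compatible with an AUC of about 0.66, and with 0.66 to 0.69 across rates from 36% to 22%. These values rest on 50 analysable recipients and on normal, equal-variance groups. They describe the borderline significant case; a larger observed difference would imply better discrimination.

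It might be inferred that a decision to use CPOi in the main trial would rest on the wrong statistic. The protocol contains no decision rule on CPOi. The only success criterion, in Section 3.3.1, is the composite proportion, which this endpoint does not touch.

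**What to change.** In the exploratory row of Section 3.3.4, add for the prediction objective the AUC of ICU-admission CPOi for PGD with a 95% confidence interval, labelled as a descriptive exploratory estimate. Keep the PGD/no-PGD differences, the comparison of the two solutions and the change over time as they are. The last two serve Secondary Objective 2 (Section 3.2) and the regression in Section 10.5, for which a group difference is the right measure.

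Optionally, report sensitivity and specificity at the cited algorithm's thresholds, written down in advance and scored against its own target of severe PGD. State that events will be few, fewer than the 18 expected for PGD of any grade.

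Add a sentence saying that CPOi shares variables and a time window with the PGD definition, so the AUC may overstate predictive value.

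The cost is a few lines of text and analysis on data already collected. The downside is wide intervals, about ±0.14 to ±0.16 at 18 against 32; these should be shown, since they guard against over-reading a significant test.

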4 TRIAL DESIGN

This is a feasibility study of a single-blind, national, multi-centre, randomised controlled trial. The purpose of the trial is to assess the methodology and feasibility of conducting an appropriately powered efficacy randomised controlled trial comparing Custodiol-HTK with St Thomas' solution for donor cardiac allograft preservation during cardiac transplantation. The design, therefore, replicates a larger efficacy randomised controlled trial, differing only in its primary outcome, as described above.

The trial will be conducted at all six UK adult cardiothoracic transplant centres. Donor hearts included in the study will be randomly allocated on a 1:1 basis to receive either Custodiol-HTK or St Thomas' solution as cardioplegia and preservative solution during the organ retrieval process. Participants (recipients of donor cardiac allografts that have received one of the above treatments as part of the random allocation process) will be blinded to their treatment allocation. It is not possible to blind the healthcare staff involved in the transplant process as the solutions have different volumes and methods of administration and are different colours. Healthcare staff who look after the recipient but were not directly involved in the transplant retrieval or implant procedures should not be informed of the treatment allocation.

5 TRIAL SETTING

The trial will be conducted at all six UK adult cardiothoracic transplant centres. These are Birmingham Queen Elizabeth Hospital, Glasgow Golden Jubilee Hospital, Manchester Wythenshawe Hospital, Harefield Hospital, Newcastle Freeman Hospital and Royal Papworth Hospital. A list of the cardiothoracic transplant units in the UK can be found at https://www.odt.nhs.uk/transplantation/cardiothoracic/cardiothoracic-transplant-units/.

London Great Ormond Street Hospital is a UK cardiothoracic transplant centre but is not participating in the study because only paediatric transplants are performed there.

All potential recipient participant recruitment and follow-up will be conducted in the UK transplant centre where they are listed to undergo their cardiac transplant.

Donor recruitment will also take place in any UK hospital that has a specialist nurse in organ donation and offers an adult cardiac allograft to the NORS.

6 PARTICIPANT ELIGIBILITY CRITERIA

6.1 Inclusion criteria

- i. Recipient population: All adult patients who are on the NHSBT waiting list for a cardiac transplant in the UK.
- ii. Donor Population: Any adult cardiac allograft donated to a UK recipient will be considered eligible.
- iii. Age:
 - (i) Recipient population: The recipient must be aged 18 or over. Recipients who turn 18 on or after the day that they receive a cardiac transplant in the UK will be eligible for inclusion provided there is sufficient time for the informed consent process to take place after midnight on the day of their 18th birthday.
 - (ii) Donor population: Any donor aged 18 or over on the day of their donation will be eligible.
- iv. Urgency Status: All categories of listing including urgent and super-urgent will be eligible.
- v. Pathology: All pathologies leading to the requirement for a heart transplant will be eligible.
- vi. Multiple transplants: Second, third or subsequent heart transplants within the same individual will be eligible provided this subsequent transplant does not occur in an emergency setting during the same hospital admission as the index heart transplant. The index transplant would remain eligible for inclusion in the trial in this case.
- vii. Multiple studies: Patients who are simultaneously enrolled in other trials will be considered eligible to take part in this study, providing the trial Protocol does not interfere with the treatment Protocols laid out in this document.

6.2 Exclusion criteria

- i. Age: Recipients under the age of 18 at the time of transplantation. Donors under the age of 18 at the time of transplantation.
- ii. Emergency re-transplant patients, where the re-transplant occurs within the same admission as the index transplant.
- iii. Patients who receive hearts procured from donation after circulatory death (DCD) donors. These patients are excluded from the study because the process of organ retrieval from DCD is very different, involving ex-situ perfusion of the beating heart with oxygenated blood, rather than maintenance of the heart in the cold arrested state with a preservative solution. The system for doing this ex-situ perfusion is called the organ care system (OCS). Currently, approximately 10% of UK heart transplants are performed using a DCD heart.
- iv. Patients who receive hearts from DBD donors procured using the organ care system device or thoracic-abdominal normothermic regional perfusion (NRP). This rarely occurs. Please note hearts procured alongside ongoing abdominal normothermic regional perfusion (which does not interfere with or alter the process for heart procurement in any way) will be eligible.
- v. Patients receiving a heart-lung block, multi-visceral transplant or other multi-organ transplant.
- vi. Donor cardiac allografts which have been offered to a UK recipient but are subsequently turned down after assessment by the NORS team.
- vii. Donor cardiac allografts where the donor family or representative have not consented for the organ to participate in research.

- viii.Donor's or recipients with a known allergy or hypersensitivity to the active ingredients or excipients of either of the IMPs. These include:
 - (i) Procaine (St Thomas' solution)
 - (ii) Disodium Edetate (St Thomas' solution)
 - (iii)Sodium Hydroxide (St Thomas' solution)
 - (iv)Potassium chloride (Both)
 - (v) Magnesium chloride hexahydrate (Both)
 - (vi)Sodium chloride (Custodiol-HTK)
 - (vii) Calcium Chloride dihydrate (Custodiol-HTK)
 - (viii) Histidine (Custodiol-HTK)
 - (ix)Histidine hydrochloride monohydrate (Custodiol-HTK)
 - (x) Tryptophan (Custodiol-HTK)
 - (xi)Mannitol (Custodiol-HTK)
 - (xii) α-Ketoglutarate (Custodiol-HTK)
 - (xiii) Potassium hydroxide (Custodiol-HTK)

6.3 Diversity and Inclusion Statement

The research team is committed to ensuring equal opportunity to participate in research. No potential participant will be denied the opportunity to participate in this study as a result of their gender, race, disability, religion or sexual orientation.

7 TRIAL PROCEDURES

See appendix 2 for a schedule of trial procedures.

7.1 Recruitment

Eligible potential transplant recipient participants will be identified by their status on a UK heart transplant waiting list. Eligible potential donor participants will be identified at the time of the offer of a donor cardiac allograft to the UK NORS. Anonymised information on potential transplant recipient participants who decline to take part, or are not randomised, will be recorded in accordance with the primary objective of this feasibility study. In accordance with the requirements for CONSORT reporting this anonymised data will include:

- i. age,
- ii. sex,
- iii. ethnicity,
- iv. the reason for declining to take part (where given),
- v. the reason not randomised.

